**Table 6-3 Dosing response to safety/tolerability events**

First Action	Result	2nd Action	Result	3rd Action
Interrupt dosing for up to two days and/or decrease dose to approximately one-half of the original starting dose for 2 weeks*†	Reduced dose tolerated	Consider increasing the dose back to the starting dose	Starting dose tolerated	Continue at starting dose until study completion
			Starting dose NOT tolerated	Decrease dose back to approximately one-half of starting dose and remain at this dose until study completion†
	Reduced dose NOT tolerated	Discontinue study treatment		

\*If the causative drug is unknown, the dose of all drugs in the combination should be reduced. If the event is believed to be causally-related to one specific drug, only the dose of that drug may need to be reduced while the other drug(s) in the combination may remain at the starting dose.

†Please refer to cohort-specific treatment information in [Section 17](#) for the exact reduced dose(s).

For some drugs that may be used in the NEXSCOT study, adverse events thought to be related to treatment are included in their reference safety information as listed in their respective IBs. Cohort-specific information ([Section 17](#)) for that particular drug should be used to determine if the individual drug could be dose interrupted and/or reduced. An example would be "Drug A" for which diarrhea is a commonly reported adverse event. In this example, in the setting of new onset diarrhea with a drug combination which includes Drug A, it may be reasonable to only dose reduce Drug A, rather than reduce the dose of all drugs in the combination.

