## 6.6 Additional treatment guidance

### 6.6.1 Treatment compliance

The investigator must promote compliance by instructing the participant to take the study treatment exactly as prescribed and by stating that compliance is necessary for the participant's safety and the validity of the study. The participant must also be instructed to contact the investigator if he/she is unable for any reason to take the study treatment as prescribed.

Compliance will be assessed by the investigator and/or study personnel at each visit using pill counts (if applicable) and information provided by the participant. This information should be captured in the source document at each visit. All study treatment dispensed and returned must be recorded in the Drug Accountability Log.

Where applicable, remote treatment administration compliance will be assessed by the OHP and information will be provided to the Investigator and/or study personnel.

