## 6 Statistical methods for Efficacy/Pharmacodynamic (PD) parameters

All participants within the efficacy/PD analysis set will be included in the efficacy/PD data analysis.

Data will be excluded from the efficacy/PD analyses in the following cases:

- For participants with protocol deviations affecting the efficacy/PD analyses, the data will be excluded as described in [Table 4-1](#) above.
- For participants that discontinued treatment early, the following *programming rule* will be applied: *Any efficacy assessments that occurred on or after the treatment discontinuation study day, will be excluded from all efficacy/PD data analyses. An exception to this is the Day 85 visit or EOS visit imaging data (MRI and MRE assessments), that will be excluded only if they occurred prior to study day 56 (i.e., imaging assessments that occurred on or after study day 56, will not be excluded from the imaging analyses).*
- Participants with <80% treatment compliance

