### Treatment compliance calculation

For each subject, the treatment compliance (%) will be calculated using the following formula:

$$100 * \left( \frac{\text{Number of capsules expected to be taken up to the last treatment day} - \text{Number of capsules missed during the treatment period}}{\text{Number of capsules expected to be taken up to the last treatment day}} \right)$$

where,

*Number of capsules expected to be taken up to the last treatment day =*  
last treatment day \* CCI , if treated with LYS006

OR

last treatment day \* CCI , if treated with LJN452

*Number of capsules missed during the treatment period =*  
Sum (Number of capsules expected to be taken in the dosing modification period x - Number of capsules actually taken in the dosing modification period x)

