#### Notes:

- The treatment compliance will be calculated separately for each treatment (LYS006 and LJN452).
- The last treatment day is defined as the last available start or end treatment day, as reflected in the dosing dataset.

- A dose modification period is a period with either a dose change or a dose interruption. These periods will be identified in the dosing dataset under records with TYPE OF CHANGE='DOSE CHANGED' and TYPE OF CHANGE='DOSE INTERRUPTED', respectively.
- For the dose modification periods:
  - Only the dosing records with non-missing dose administered, non-missing start date and non-missing end date will be considered in the calculations.
  - Dose administered = Number of capsules administered
  - The number of capsules expected to be taken in a dosing modification period =  
(period end day – period start day +1) \* CCI , if treated with LYS006  
OR  
(period end day – period start day +1) \* CCI , if treated with LJN452
  - The number of capsules actually taken in a dosing modification period =  
(period end day – period start day +1) \* dose administered
  - The frequency of dose administered will not be considered in the calculations, only the dose administered itself.

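### The SAP compliance formula gives no visible credit for dose reductions or interruptions the protocol permits, so a participant who follows the protocol can fall below 80% and lose all efficacy/PD data

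*SAP*

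**What the plan says.** SAP section 6 names three cases in which data leave the efficacy/PD analyses: the protocol deviations in Table 4-1, early treatment discontinuation, and "Participants with <80% treatment compliance". The third has no further condition.

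The denominator of the compliance percentage is "Number of capsules expected to be taken up to the last treatment day", computed as the last treatment day times a redacted factor for each drug. Missed capsules are the sum, over dose modification periods, of capsules expected minus capsules taken. The notes state: "A dose modification period is a period with either a dose change or a dose interruption". Expected capsules in such a period are its length in days times a redacted per-drug factor. Capsules taken are its length times the recorded dose, where dose means number of capsules. The notes add: "The frequency of dose administered will not be considered in the calculations, only the dose administered itself". Compliance is calculated separately for LYS006 and LJN452.

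Protocol 6.5.1 permits dose changes and interruptions for safety. Table 6-3 starts with an interruption of up to two days and/or about half dose for two weeks. If the starting dose is then not tolerated again, its third action is: "Decrease dose back to approximately one-half of starting dose and remain at this dose until study completion". Table 16-1 footnote e allows restart after an interruption of less than 10 days and asks the investigator to consider a reduced dose. Protocol 6.6.1 has the investigator promote compliance by "instructing the participant to take the study treatment exactly as prescribed".

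**The concern.** The expected count has no visible branch for a reduced prescribed dose or a directed interruption. A participant who takes every capsule prescribed during a permitted modification can then accumulate missed capsules. Below 80%, the plain reading of the bullet removes that participant altogether, including visits before the modification.

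Such an exclusion depends on tolerability after treatment began, and it discards observed ELF, ALT and liver-fat values. Protocol 17.1.1.3 uses LYS006 alone against the combination to judge whether effects are additive, synergistic or antagonistic. With about 20 evaluable participants per arm (protocol section 5), each full exclusion is about 1/20 = 5% of an arm.

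**Working it through.** The documents give no worked compliance figure to reproduce, so the check applies the SAP formula to courses the protocol permits.

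**Inputs.**
- Treatment runs from Day 1 to Day 85 (protocol section 3), so the last treatment day for a completer is L = 85.
- The reduced dose is about one-half (Table 6-3).
- The longest whole-day interruption after which restart is allowed is 9 days (Table 16-1 footnote e).
- Assumptions: the redacted factor c is the same full-dose count in both expected-capsule expressions, and recorded doses are on the same scale; the reduced dose is a fraction f of the full-dose capsules; an interruption is recorded as zero capsules.

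**Formula.** Expected = L × c. Missed = c × [(1 − f) × reduced days + days off]. The factor c cancels:

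compliance = 100 × {1 − [(1 − f) × reduced days + days off] / L}

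**Results with f = 0.5.** The third-action row assumes reduced dose on Days 15–28 (14 days), full dose on Days 29–35, and reduced dose on Days 36–85 (50 days), which gives 64 reduced days.

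| Course | Calculation | Score | Outcome |
|---|---|---|---|
| Completer, one 14-day reduction | 1 − 7/85 | 91.8% | kept |
| Completer, 34 reduced days | 1 − 17/85 | 80.0% | kept |
| Completer, 35 reduced days | 1 − 17.5/85 | 79.4% | excluded |
| Third action from Day 15, 64 reduced days | 1 − 32/85 | 62.4% | excluded |
| Completer, 9 days off only | 1 − 9/85 | 89.4% | kept |
| Completer, 9 days off + 16 reduced days | 1 − 17/85 | 80.0% | kept |
| Completer, 9 days off + 17 reduced days | 1 − 17.5/85 | 79.4% | excluded |
| 9 days off only, last treatment day 44 | 1 − 9/44 | 79.5% | excluded |
| 9 days off only, last treatment day 45 | 1 − 9/45 | 80.0% | kept |

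The rows with days off only do not use f.

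**Sensitivity.** The documents say only that the reduced dose is approximately one-half, so the following range is an assumption. At f = 0.4, exclusion of a completer starts at 29 reduced days and the third-action course scores 1 − 38.4/85 = 54.8%. At f = 2/3, exclusion starts at 52 reduced days and the same course scores 1 − 21.3/85 = 74.9%. With L = 84 and f = 0.5, exclusion starts at 34 reduced days (79.8%). If a reduction is made by a lower-strength capsule or by frequency alone, the recorded count is unchanged and the score stays at 100%.

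**Prescribed-dose denominator.** On the third-action course with f = 0.5, expected capsules per unit of c are 21 + 64 × 0.5 = 53. A participant who takes all of them scores 53/53 = 100%.

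**The case against.** The strongest objection is redaction. Reduced doses and capsule factors cannot be read, so the public text cannot show that any reduction lowers the score. For reductions this stands in full. Permitted interruptions do not need the fewer-capsules assumption, but they need zero-capsule records, and alone they matter only with an early stop. In the Day 44 example liver fat is not at stake, because an end-of-treatment MRI is required only for discontinuation on or after Week 8.

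A second objection is that the sponsor may want an analysis of participants adequately exposed to the planned dose. The TRT03 footnote in SAP Table 4-1, which makes interruptions over 2 days or reductions over 2 weeks exclusionary, fits that pattern. This is a legitimate question, so the 80% analysis need not be dropped. However, TRT03 concerns modification guidelines that were not followed and removes data only from the deviation day. It neither justifies nor cures the scoring of permitted courses as missed. Protocol 6.6.1 does not settle the matter either: it is an instruction to promote compliance and defines no formula.

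Third, the study is non-confirmatory, with 80% intervals on secondary endpoints. This stands and limits the severity.

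A reader might infer more than the text supports in three places:
- That the 80% bullet contradicts the discontinuation bullet ("Any efficacy assessments that occurred on or after the treatment discontinuation study day, will be excluded from all efficacy/PD data analyses"). It does not. The bullets are separate grounds for exclusion, and the second nowhere protects earlier visits from another rule. They add together.
- That the missing start day is itself an error. Compliance is one whole-period number and the bullet names participants, so there is no event day to attach.
- That the rule favours one arm. Arm 2 has two compliance values per participant, but the visible SAP does not say how they combine, and the Programming Datasets Specification mentioned in SAP 1.1 may do so.

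**Conclusion.** The point holds conditionally. On its visible text, the formula gives no credit for permitted modifications, and the rule then removes the participant's efficacy/PD data because of a tolerability outcome. At half the capsules, a completer is affected only when reduced days exceed 40% of treatment days (35 or more of 85), or after a shorter reduction combined with an interruption. A single two-week reduction in a completer is safe.

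The size rests on three unverified assumptions: the same full-dose factor throughout, fewer capsules at the reduced dose, and zero-capsule records for interruptions. The number of participants affected and the direction of any bias cannot be determined. The primary safety analysis is unaffected. The severity lies between minor and should-fix: the correction is cheap and the exposure is limited but real.

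**What to change.** Compute expected capsules from the dose prescribed in each period, so that modifications permitted by Table 6-3 or by protocol Sections 16.1 and 16.2 are not counted as missed. Repeat the ELF, ALT and liver-fat models in all dosed participants with data, regardless of compliance, and report both sets of results.

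Two clarifications should go in at the same time. State whether compliance below 80% on either drug, on both, or on an average excludes an Arm 2 participant. The choice matters: if only one drug follows the third-action course, the values are 62.4% and 100%, with a mean of 81.2%, so only the either-drug reading excludes. Also reconcile the TRT03 footnote with Table 6-3, since the table contains a reduction longer than two weeks. No change to any dosing rule is implied.

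The cost is one derivation change, one extra set of model runs and some SAP wording. The downside is that the added estimates mix full-dose and reduced-dose exposure, which is why both sets should be shown.

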### Treatment compliance calculation

For each subject, the treatment compliance (%) will be calculated using the following formula:

$$100 * \left( \frac{\text{Number of capsules expected to be taken up to the last treatment day} - \text{Number of capsules missed during the treatment period}}{\text{Number of capsules expected to be taken up to the last treatment day}} \right)$$

where,

*Number of capsules expected to be taken up to the last treatment day =*  
last treatment day \* CCI , if treated with LYS006

OR

last treatment day \* CCI , if treated with LJN452

*Number of capsules missed during the treatment period =*  
Sum (Number of capsules expected to be taken in the dosing modification period x - Number of capsules actually taken in the dosing modification period x)

#### Notes:

- The treatment compliance will be calculated separately for each treatment (LYS006 and LJN452).
- The last treatment day is defined as the last available start or end treatment day, as reflected in the dosing dataset.

- A dose modification period is a period with either a dose change or a dose interruption. These periods will be identified in the dosing dataset under records with TYPE OF CHANGE='DOSE CHANGED' and TYPE OF CHANGE='DOSE INTERRUPTED', respectively.
- For the dose modification periods:
  - Only the dosing records with non-missing dose administered, non-missing start date and non-missing end date will be considered in the calculations.
  - Dose administered = Number of capsules administered
  - The number of capsules expected to be taken in a dosing modification period =  
(period end day – period start day +1) \* CCI , if treated with LYS006  
OR  
(period end day – period start day +1) \* CCI , if treated with LJN452
  - The number of capsules actually taken in a dosing modification period =  
(period end day – period start day +1) \* dose administered
  - The frequency of dose administered will not be considered in the calculations, only the dose administered itself.

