## 4 Statistical methods: Analysis sets

The **safety analysis set** will include all participants that received any study drug.

The **PK analysis set** will include all participants with at least one available valid (i.e., not flagged for exclusion) PK concentration measurement, who received any study drug and with no protocol deviations that impact on PK data.

The **efficacy/PD analysis set** will include all participants with available efficacy/PD data and no protocol deviations with relevant impact on efficacy/PD data.

For all analysis sets, participants will be analyzed according to the study treatment(s) received.

Throughout this document, 'treatment' refers to the treatment arm of a cohort that each participant is assigned to.

For treatments with an extended half-life, EOS1 will be required as a standard, non-EOS post-treatment follow up visit, and EOS2 will serve as the EOS visit. For all other treatments, EOS1 will serve as the EOS visit. If a participant discontinues study treatment early, the participant should be scheduled for a subsequent visit at which time all assessments at the EOS1 visit should be performed. For treatments with an extended half-life, if a participant discontinues

early after EOS1, then the participant should be scheduled for a subsequent visit at which time all assessments at the EOS2 visit should be performed.

The Day 113 (EOS1) visit for treatments with no extended half-lives and the Day 141 (EOS2) visit for treatments with extended half-lives will be pooled and reported/analyzed together under a common EOS visit, labeled as 'EOS', in the reporting/analysis. The Day 113 (EOS1) visit for treatments with extended half-lives will be reported/analyzed as a distinct visit, labeled as 'Day 113', in the reporting/analysis.

For the End of Study (EOS) visit, only data from study completers will be included in the efficacy summary/analysis tables/figures. Safety summary/analysis tables/figures will include data from all participants, i.e., both study completers and non-study completers for the End of Study (EOS) visit.

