## 4.1 Cohort-specific information:

### 4.1.1 Cohort 1:

Cohort 1 will evaluate the use of LYS006 alone and tropifexor (LJN452) in combination with LYS006 for the treatment of elevated liver fat, liver inflammation and liver fibrosis in NAFLD participants who manifest a NASH-like biomarker phenotype. The drug combination of LYS006 and tropifexor (LJN452) may provide clinical benefit beyond that of either drug alone, considering different, complementary mechanisms of action of these drugs.

Approximately 50 participants will be randomized in a 1:1 ratio to one of the following treatment arms:

- Treatment arm 1: LYS006 Commercially Confidential Information
- Treatment arm 2: Tropifexor (LJN452) Commercially Confidential Information + LYS006 Commercially Confidential Information

The treatments used in cohort 1 (i.e. LYS006 and Tropifexor) do not have extended half-lives, so the EOS1 visit will serve as the end-of-study visit for participants randomized to any of the two treatment arms of cohort 1 (i.e. for all cohort 1 participants).

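### The SAP does not say how two per-drug compliance values in the combination arm decide the below-80% exclusion, so the efficacy filter differs by arm, and no modelled analysis without it is visible

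*SAP*

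**What the plan says.** SAP 6 opens its list of exclusions with "Data will be excluded from the efficacy/PD analyses in the following cases", and the last item is "Participants with <80% treatment compliance". The compliance formula that follows gives a percentage for each subject. The notes then say: "The treatment compliance will be calculated separately for each treatment (LYS006 and LJN452".

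Missed capsules are the expected minus the actual count, summed over dose modification periods. The notes define these: "A dose modification period is a period with either a dose change or a dose interruption". The expected count uses a fixed number of capsules per day for each drug (value redacted), so a shortfall during a permitted reduction counts as missed.

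The footnote to Protocol Table 6-3 lets the two drugs part company. If one drug is thought to be the cause, "only the dose of that drug may need to be reduced while the other drug(s) in the combination may remain at the starting dose".

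Two other SAP 4 statements bear on this. The efficacy/PD set is "all participants with available efficacy/PD data and no protocol deviations with relevant impact on efficacy/PD data", with no compliance threshold. The general convention is "Throughout this document, 'treatment' refers to the treatment arm of a cohort that each participant is assigned to", which does not match the per-drug use in the compliance notes. The 80% rule is also absent from Protocol 6.6.1, Protocol 12.1, SAP Table 4-1 and the visible items of SAP 11.

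**The concern.** An Arm 1 participant (LYS006) has one value to set against 80%. An Arm 2 participant (LYS006 plus tropifexor) has two. The SAP could mean that failing either drug excludes, that both must fail, or that some combined value is used. Nothing visible settles it.

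The filter acts after randomisation and follows dose changes and interruptions, which are consequences of the assigned treatment. Arm 1 has no tropifexor modifications to count. Protocol 17.1.1.3 gives comparison with the combination as a reason for having the LYS006 arm, to judge how the two agents act together. As planned, that comparison is made in subsets whose selection depends on the arm.

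The missing-at-random argument in SAP 6.2.3.1 does not help. The MMRM borrows from a participant's other values, but this exclusion names participants and so removes those values too. The optional last-observation-carried-forward analysis does not lift the filter. The study is also open label, so a rule left unstated could be settled by people who can already see results by arm.

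**Working it through.** **The plan's own figure.** Protocol 5 gives about 25 enrolled per arm. Two arms give 2 x 25 = 50, which agrees with SAP 4.1.1: "Approximately 50 participants will be randomized in a 1:1 ratio to one of the following treatment arms". No alpha, power, effect size or SD is visible, so no sample-size formula can be checked.

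**Can the two values differ within one participant?** The formula is 100 x (expected - missed) / expected. Assume 84 days of dosing and that a reduction halves the capsule count (the actual counts are redacted).

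- 14 days at half dose: 100 x (84 - 7) / 84 = 91.7%, kept.
- 34 days at half dose: 100 x (84 - 17) / 84 = 79.8%, below the line. Seventeen days of full interruption give the same value.
- One drug at half dose from Day 15 to Day 84 (70 days): 100 x (84 - 35) / 84 = 58.3% for that drug and 100% for the other. This participant is excluded if either value decides and kept if both must fail. An equal-weight average is (58.3 + 100) / 2 = 79.2%, which excludes.

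So one dosing record can lead to opposite decisions, depending on the unstated rule.

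**How many participants?** Let q be the chance that compliance with a given drug is below 80%. The documents give no value; 5-15% is an assumption, taken as equal for both drugs. The exclusion probability in Arm 1 is q. In Arm 2 it is:

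- either drug excludes, failures independent: 1 - (1 - q)^2
- failures fully coincide: q
- both must fail, failures independent: q^2

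Expected losses out of 25:

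| q | Arm 1 | Arm 2, either, independent | Arm 2, fully coincident | Arm 2, both, independent |
|---|---|---|---|---|
| 5% | 1.25 | 2.44 | 1.25 | 0.06 |
| 10% | 2.50 | 4.75 | 2.50 | 0.25 |
| 15% | 3.75 | 6.94 | 3.75 | 0.56 |

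**Effect on the arm contrast.** If excluded participants differ from kept ones by d log units, by the same amount in both arms, the filtered contrast moves by (difference in exclusion fraction) x d. Under independence the absolute difference is q - q^2 for either rule, with opposite signs. Assume d = 0.26, about 30% on the ALT scale because exp(0.26) = 1.30.

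- q = 5%: 0.0475 x 0.26 = 0.012, about 1%
- q = 10%: 0.0900 x 0.26 = 0.023, about 2%
- q = 15%: 0.1275 x 0.26 = 0.033, about 3%
- fully coincident failures: 0

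**The case against.** The best defence is that requiring at least 80% of each assigned component is one rule, adherence to the assigned regimen, applied to both arms. An analysis of adherent participants is a legitimate choice in a non-confirmatory study with no primary efficacy objective and 80% intervals. Failures may also coincide: the Protocol Table 6-3 footnote has all drugs reduced when the cause is unknown, and with full coincidence the arms lose equal numbers. A shift of about 3% is small beside the reductions of at least 30% in ALT and liver fat that Protocol 4.1.3 associates with high efficacy.

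Most of this stands, and it limits how much the point matters. It does not supply the missing rule or show what the comparison looks like without the filter.

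The same evidence rules out three stronger readings that a reader might infer.

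- *The combination arm is filtered harder.* That follows only if failing either drug excludes and failures do not coincide. The SAP does not say so, and if both drugs must fail Arm 2 could be filtered less.
- *No unfiltered efficacy results will exist.* Parts of SAP 3, 6.2.3 and 11 are redacted, so only the visible text can be judged. ALT, glucose, HbA1c and lipids also appear in the safety-set laboratory summaries without this filter, though only descriptively and without ELF or liver fat.
- *The planned fall from 25 enrolled to about 20 evaluable per arm is due to this filter.* The documents do not attribute that loss to compliance.

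**Conclusion.** The point holds in this form. The exclusion is computed per drug, its decision rule for Arm 2 is undefined, and selection into the efficacy comparison depends on arm and tolerability. No modelled analysis of ELF, ALT or liver fat without the filter is visible.

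The direction of any bias cannot be stated and its size is unknown. Over the assumed 5-15% failure rate, Arm 2 could lose anything from 0.1 to 6.9 of 25, against 1.3 to 3.8 in Arm 1. The contrast then shifts by at most about 3%. That bound rests on the assumed failure rates and on a 0.26 log-unit difference that is equal in the two arms; if the difference varies by arm, the bound does not apply. With efficacy secondary and the study non-confirmatory, this is a cheap improvement to make before database lock. It does not invalidate the plan.

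**What to change.** In SAP 6:

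1. State before database lock how the two Arm 2 values determine exclusion in the filtered analysis.
2. Beside the filtered analysis, run the same MMRM and ANCOVA models on all dosed participants with available efficacy/PD data, regardless of compliance. Compare randomised participants by assigned arm, and note that this departs from the treatment-received rule in Protocol 12.1 and SAP 4. Participants enrolled without randomisation (Protocol 6.3.2) do not belong in that comparison.
3. State whether the added analysis includes values after treatment discontinuation, which SAP 6 otherwise excludes apart from later imaging.

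Filtering both arms on LYS006 compliance alone would not do instead. In Arm 2 that compliance also arises after randomisation and can be affected by tropifexor.

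The cost is SAP wording and one further run of existing models on data already collected. The added estimate will be diluted by poor adherence, which is why both should be shown. It will not restore every participant: for early discontinuers, Protocol 8.3.3 requires an end-of-treatment MRI only from Week 8 onwards.

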e Study drug must be interrupted (date of last study drug dose must be recorded in the eCRF). The sponsor should be notified of laboratory abnormalities and any clinical symptoms, and participants should be closely monitored until resolution of clinical symptoms/stabilization of liver biochemistries to baseline levels or baseline grade of abnormality. In participants with elevations in liver biochemistry but who do not meet permanent drug discontinuation criteria, study drug may be resumed if it is determined that complete resolution to normal or clinically comparable to baseline levels or baseline grade of abnormality (baseline value will be calculated as the mean of the last two assessments before first administration of the study drug) has occurred and it is not considered that the deterioration in liver function was related to study drug. This must be documented based on biochemical parameters and clinical symptoms, per the discretion of the investigator and in consultation with the sponsor. Restarting study drug is only permitted following an interruption of less than 10 days. The investigator should consider restarting study drug treatment at a reduced dose if possible. If significant liver abnormalities recur at any time after restarting study drug, then study drug must be permanently discontinued.

f In participants with emerging evidence of Gilbert's syndrome, in place of the total bilirubin criterion, use direct bilirubin  $> 2 \times$  baseline.

g Development of liver-related clinical symptoms in absence of biochemical abnormalities is an indication for prompt biochemical and physical evaluation to decide whether continued dosing is appropriate. If prompt evaluation is not possible, study drug should be interrupted and participant followed for laboratory monitoring and causality evaluation.

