## 16.2 Appendix 2: Renal safety monitoring

Recommended actions and follow-up assessments regarding renal function data are shown in [Table 16-2](#). If evaluation of a renal event reveals a reversible etiology not related to study drug, the study drug may be restarted as long as the period of interruption is less than 10 days.

Note that the day to day variability of a particular participant's serum creatinine is reflected in the different values measured at screening versus baseline. Because of this, the investigator should use the higher of these two values as the reference against which to compare on-treatment serum creatinines.

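### SAP compliance score: a closed, never-resumed dose interruption counts as missed capsules, so a fully compliant early stopper can fall below 80% and lose all efficacy/PD data

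*SAP*

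**What the plan says.** SAP Section 6 lists the cases in which data leave the efficacy/PD analyses. Two matter here.

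- Early discontinuation: "Any efficacy assessments that occurred on or after the treatment discontinuation study day, will be excluded from all efficacy/PD data analyses". Imaging from study day 56 onwards is exempt. Earlier assessments stay in.
- Low compliance: "Participants with <80% treatment compliance". This bullet has no start day.

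Under Treatment compliance calculation, expected capsules are the last treatment day times the daily count (redacted). Missed capsules are summed over dose modification periods. The notes add three rules:

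- Where the denominator ends: "The last treatment day is defined as the last available start or end treatment day, as reflected in the dosing dataset". Nothing limits this to days on which capsules were taken.
- Which periods feed the missed count: "A dose modification period is a period with either a dose change or a dose interruption". Both kinds are picked out of the dosing data by their type of change.
- Which of those records are usable: "Only the dosing records with non-missing dose administered, non-missing start date and non-missing end date will be considered in the calculations".

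The score is calculated separately for LYS006 and LJN452. By contrast, the COMD01 and TRT03 rows of SAP Table 4-1 exclude data only from the day of the deviation.

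Protocol 16.1 (Table 16-1, footnote e) states: "Restarting study drug is only permitted following an interruption of less than 10 days". Protocol 16.2 has a similar limit for renal events: "the study drug may be restarted as long as the period of interruption is less than 10 days". An interruption that turns into a permanent stop is therefore a path the protocol itself creates.

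**The concern.** A compliance threshold should remove people who did not take the drug while they were meant to be on it. Here the denominator can run past the last dose, to the end of an off-drug period ordered for safety. Someone who missed nothing while on treatment can then be classed as non-compliant.

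The loss is total. The early-discontinuation rule would keep such a participant's on-drug ALT, ELF and weight values, and the undated compliance bullet deletes them. It also weakens the missing-at-random argument in SAP 6.2.3.1, because that argument relies on each participant's observed values. For a liver-related stop, the exclusion may depend on ALT itself, which is a secondary efficacy endpoint.

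**Working it through.** The plan gives no worked compliance figure, so there is nothing to reproduce first.

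**Inputs.** From SAP Section 6: the formula, the 80% threshold, the definition of last treatment day and the completeness filter. From Protocol 16.1 and 16.2: the 10-day restart limit. From Protocol Section 5: about 25 enrolled and 20 evaluable per arm. Assumed, because the documents give no such figures: D fully dosed days, then an interruption of L days at zero capsules, never resumed.

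**Formula, closed record.** Let c be the daily capsule count.

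- Last treatment day = D + L
- Expected = (D + L) × c
- Missed = L × c
- Score = [(D + L)c − Lc] / [(D + L)c] = D/(D + L)

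The redacted c cancels. D/(D + L) < 0.80 is equivalent to L > D/4.

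| D | L | Calculation | Score | Below 80%? |
|---|---|---|---|---|
| 14 | 7 | 14/21 | 66.7% | yes |
| 21 | 7 | 21/28 | 75.0% | yes |
| 28 | 7 | 28/35 | 80.0% | no |
| 28 | 10 | 28/38 | 73.7% | yes |
| 29 | 10 | 29/39 | 74.4% | yes |
| 39 | 10 | 39/49 | 79.6% | yes |
| 40 | 10 | 40/50 | 80.0% | no |
| 56 | 14 | 56/70 | 80.0% | no |
| 56 | 15 | 56/71 | 78.9% | yes |

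A 2-day record catches only D of 7 or less. A record closed at Day 85 catches D of 67 or less (67/85 = 78.8%; 68/85 = 80.0%). In the last row of the table, the participant would also lose imaging from day 56 onwards that the early-discontinuation rule deliberately keeps.

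**Same exposure, other data entry.**

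- Interruption record with no end date: the completeness filter drops it, so missed = 0. With D = 29, its start on day 30 sets the last treatment day, and the score is 30c/30c = 100%.
- Permanent stop dated at the last dose, with no interruption record: 29c/29c = 100%.

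**Alternative reading of last treatment day.** Suppose it means the last dosed day. The formula still sums missed capsules over every modification period, so the score is (D − L)/D. For D = 29 and L = 10 that is 19/29 = 65.5%, which is lower still.

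**Scale.** One excluded participant is 1/20 = 5% of the evaluable arm, or 1/25 = 4% of those enrolled.

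**The case against.** The strongest reply is that several conditions must coincide. The interruption must be closed with an end date and a zero dose, although one that never resumes has no natural end date; left open, it scores 100%. It must also exceed a quarter of the dosed days. In Table 16-1 the largest ALT and AST rises go straight to permanent discontinuation, with no interruption required first, so those participants can score 100%. The SAP also places derived-variable detail in a programming specification that is not available here. All of this stands, and it limits how often the problem occurs. It does not remove it: the SAP does not say how a never-resumed interruption is closed, and reading the definition as the last dosed day makes the score worse.

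A reader might infer that the rule visibly inflates the ALT effect. For example, take 18 participants at 0.80 × baseline and two liver-stopped participants at 2.5 × baseline. The geometric mean ratio is exp[(18 ln 0.80 + 2 ln 2.5)/20] = 0.90 with the two kept and 0.80 without them. The documents do not support using this as an estimate. Every input is assumed. At 2.5 × baseline without symptoms or the bilirubin or INR criteria, Table 16-1 can keep the participant on dosing. Early stoppers' ALT from the discontinuation day onwards is dropped under either rule, so such a contrast could arise directly only at an early visit. At Week 12 any effect would be indirect, through the MMRM.

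A reader might also infer that everyone removed this way was stopped for a liver or renal signal. Protocol 6.5.1 also allows interruption for general intolerance.

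**Conclusion.** The point holds in a conditional form. As written, a fully compliant participant with a closed, zero-dose, never-resumed interruption longer than D/4 scores below 80% and loses all efficacy/PD data. With a 10-day record this applies to anyone with 39 or fewer dosed days. Identical exposure entered differently scores 100%, so membership of the analysis depends on a data-entry convention that neither document states.

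This rests on reading the undated exclusion bullet literally, as reaching back over all visits. The SAP also does not say which drug's score decides in the combination arm.

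The reach is limited. Only secondary efficacy/PD analyses of a non-confirmatory study are affected; the primary safety analysis is untouched, and ALT is still summarised there. The number of participants affected cannot be computed from the documents. Bias in favour of the regimen is plausible for liver-related stops at early ALT visits, but it is not established for renal or general intolerance stops.

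**What to change.** In the notes to the SAP compliance calculation, define the last treatment day, for this calculation only, as the last day on which a non-zero number of capsules of that drug was taken. Leave interruption days after that day out of both expected and missed capsules. Both parts are needed: changing the definition alone gives the 65.5% result above. With both, every scenario in the table scores 100%, and interruptions that are followed by resumed dosing still count as missed.

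Leave the treatment discontinuation study day in SAP Section 6 unchanged, so that the early-discontinuation rule alone decides which of these participants' assessments are kept. Redefining discontinuation as the first day of the interruption would move that cut-off earlier and could drop values collected during the interruption that are now kept.

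The cost is a short SAP amendment before database lock and a small program change. A few early stoppers would stay in the early-visit analyses, and the reported effect may look slightly less favourable. No clinical rule changes.
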